8.3.1 Inclusion Criteria

Investigators should ensure that all trial enrollment criteria have been met at screening. If a patient's status changes (including laboratory results or receipt of additional medical records) after screening but before the first dose of trial drug is given such that they no longer meet all eligibility criteria, they should be excluded from participation in the trial.

Patients **MUST** satisfy all of the following entry criteria before they will be allowed to participate in the trial:

1. For the Dose Escalation part: Patients with relapsed, advanced and/or metastatic cancer of the ovary, cervix, endometrium, bladder, prostate, esophagus or NSCLC who have failed available standard treatments or who are not candidates for standard therapy.

Final 5.0 (incorporating Protocol Amendment 4)
06 Jul 2017

For the Cohort Expansion part: The specific indications for the Cohort Expansion part will be decided once the RP2D has been determined. After implementation of the urgent safety measure (Protocol Amendment 4), no patients will further receive the 3q4wk schedule; instead, tisotumab vedotin (HuMax-TF-ADC) 2.0 mg/kg will be administrated once q3wk.

- Patients with relapsed, advanced and/or metastatic cancer of the ovary, cervix, endometrium, bladder, prostate, esophagus, or NSCLC who have failed the following anticancer therapy:
 - o Bladder cancer (including urothelial carcinomas [transitional cell carcinomas] regardless initial site of origin of the tumor: renal pelvis, ureter or bladder lumen): failing platinum-based therapy. Patients must have received no more than three prior treatment regimens for advanced disease.
 - o CRPC: failing docetaxel and either abiraterone OR enzalutamide. Patients must have received no more than two prior chemotherapy-based regimens and a maximum of six prior treatment regimens for advanced disease.
 - Ovarian cancer: resistant to at least one platinum-based therapy and after failing at least one line of taxane-containing therapy (isolated CA 125 progression does NOT qualify for trial entry). Patients with primary platinum refractory disease are excluded. Patients must have received no more than five prior treatment regimens for advanced disease.
 - o Cervical cancer: failing a platinum-based regimen. Patients must have received no more than four prior treatment regimens for advanced disease.
 - Endometrial cancer: failing platinum-based therapy. Patients must have received no more than four prior treatment regimens for advanced disease (excluding adjuvant chemotherapy).
 - Esophageal cancer (esophageal cancer or gastro-esophageal junction cancer): failing platinum-based therapy with or without taxanes depending on established SoC therapy. Patients must have received no more than three prior treatment regimens for advanced disease.
 - o NSCLC: failing at least one platinum-based regimen. Patients with epidermal growth factor receptor (EGFR) or anaplastic lymphoma kinase mutations should have been treated with appropriate targeted therapy before trial entry. Patients must have received no more than four (five allowed for patients with EGFR mutated adenocarcinomas) prior treatment regimens for advanced disease.

Other inclusion criteria:

- 2. Patients must have measurable disease according to RECIST (Response Evaluation Criteria In Solid Tumors) version 1.1 (Eisenhauer et al., 2009).
 - o A minimum of one lesion ≥ 10 mm in the longest diameter (LD) from a non-irradiated area. If target lesion(s) are located within previously irradiated area

Final 5.0 (incorporating Protocol Amendment 4)

only, the patient can be enrolled only if there has been demonstrated progression in the "in field" lesion and after sponsor acceptance.

- Lymph nodes lesion ≥ 15 mm in the shortest diameter from a non-irradiated area.
- Patients with prostate cancer must be clinically refractory and resistant to hormone therapy as documented by progression (CRPC) and can be included based on PSA and/or bone metastases according to the Prostate Cancer Working Group Guideline (Scher et al., 2008).
- Patients with ovarian cancer can be included based on CA 125 positivity according to the Gynaecologic Cancer Intergroup Guideline (Rustin et al., 2004). This is only applicable for the Dose Escalation part of the trial.
- 3. Age \geq 18 years.
- 4. Acceptable renal function defined as:
 - o Glomerular filtration rate (Cockroft-Gault) > 45 mL/min.
- 5. Acceptable liver function defined as:
 - Alanine aminotransferase (ALT) and aspartate aminotransferase (AST) ≤ 3 times the upper limit of normal (ULN); if liver tumor/metastases are present, then < 5 × ULN is allowed.
 - o Bilirubin \leq 1.5 × ULN, except in patients diagnosed with Gilbert's syndrome, direct bilirubin \leq 2 × ULN.
- 6. Acceptable hematological status (hematologic support is allowed if administered at least one week before Cycle 1 Day 1) defined as:
 - Hemoglobin \geq 5.6 mmol/L (\sim 9 g/dL).
 - Absolute neutrophil count (ANC) $\geq 1500/\mu L$ (1.5 ×10⁹/L).
 - Platelet count $\geq 100 \times 10^9$ /L.
- 7. Acceptable coagulation status defined as:
 - o INR ≤ 1.2 (without anticoagulant therapy).
 - \circ aPTT \leq ULN.
- 8. Eastern Cooperative Oncology Group (ECOG) performance status of 0 or 1.
- 9. Life expectancy of at least three months.
- 10. A negative serum pregnancy test (if female and aged between 18-55 years old).
 - Women who are pregnant or breast feeding are not to be included.
- 11. Patients, both females and males, of reproductive potential must agree to use adequate contraception during and for six months after the last infusion of tisotumab vedotin (HuMax-TF-ADC).

Final 5.0 (incorporating Protocol Amendment 4) 06 Jul 2017

- Adequate contraception for women is defined as hormonal birth control or an intrauterine device (see Section 10.16.6). In countries where two highly effective methods of contraception are required this will be an inclusion criterion (refer to Appendix 2).
- Male patients must be willing to use a latex condom during any sexual contact with females of childbearing potential during and for six months after the last infusion of tisotumab vedotin (HuMax-TF-ADC), even after having undergone a successful vasectomy. It is recommended that fertile males consider having a semen specimen obtained for storage for potential future conception.
- 12. Following receipt of verbal and written information about the trial, patients must provide signed informed consent before any trial-related activity is carried out.

8.3.2 Exclusion Criteria

If any of the following apply, the patient **MUST NOT** enter the trial:

Hematological

- 1. Known past or current coagulation defects leading to an increased risk of bleeding.
- 2. Diffuse alveolar hemorrhage from vasculitis.
- 3. Known bleeding diathesis.
- 4. Ongoing major bleeding, defined as:
 - Symptomatic bleeding in critical area organ, such as intracranial, intraocular, retroperitoneal, intra-articular or pericardial, or intramuscular with compartment syndrome; and/or
 - o Bleeding causing a drop in hemoglobin level of 2 g/dL (1.24 mmol/L) or more, or bleeding leading to transfusion of two or more units of whole blood or red cells.
- 5. Trauma with increased risk of life-threatening bleeding or history of severe head trauma or intracranial surgery within two months of trial entry.

Cardiovascular

- 6. Have clinically significant cardiac disease, including:
 - Unstable angina
 - o Acute myocardial infarction within six months of the Screening Visit
 - Known congestive heart failure (Grade III or IV as classified by the New York Heart Association); and/or a known decreased cardiac ejection fraction of < 45%
- 7. A baseline QT interval as corrected by Fridericia's formula (QTcF) > 450 msec, a complete left bundle branch block (defined as a QRS interval ≥ 120 msec in left bundle branch block form) or an incomplete left bundle branch block.

Excluded medications or treatment regimens

8. Therapeutic anti-coagulative or long-term anti-platelet treatment.

Final 5.0 (incorporating Protocol Amendment 4) 06 Jul 2017

 Use of low dose acetylsalicylic acid (ASA) up to 81 mg/day and non-ASA nonsteroidal anti-inflammatory drugs (NSAIDs) is allowed.

9. Have received:

- a. Granulocyte colony stimulating factor (G-CSF) or granulocyte/macrophage colony stimulating factor support within one week before the Screening Visit or
- b. Pegylated G-CSF within two weeks before the Screening Visit, or
- c. Blood transfusion and/or erythropoietin within one week before first dose.
- 10. Have received a cumulative dose of corticosteroid \geq 150 mg (prednisone or equivalent doses of corticosteroids) within two weeks before the first infusion.
- 11. No dietary supplements allowed during the trial period, except multivitamins, vitamin D and calcium unless approved by the sponsor Medical Officer.

Surgery/procedures

- 12. Major surgery within six weeks or open biopsy within 14 days before drug infusion.
- 13. Plan for any major surgery during treatment period.
- 14. Patients not willing or able to have a pre-trial tumor biopsy taken (the screening biopsy can be omitted if archived material is available).
- 15. Presence or anticipated requirement of epidural catheter in relation to infusions (within 48 hours before and after dose of trial drug).

Central nervous system

- 16. Any history of intracerebral arteriovenous malformation, cerebral aneurysm, brain metastases or stroke.
 - o Transient ischemic attack > one month prior to screening is allowed.

Prior therapy

- 17. Any anti-cancer therapy including small molecules, immunotherapy, chemotherapy monoclonal antibodies or any other experimental drug within four weeks or five half-lives, whichever is longest, before first infusion. For anti-cancer therapies with half-lives > 8 days, a washout period of at least 28 days is acceptable.
- 18. Prior treatment with bevacizumab within 12 weeks before the first infusion.
- 19. Any prior therapy with a conjugated or unconjugated auristatin derivative.
- 20. Radiotherapy within 28 days prior to first dose.
- 21. Patients who have not recovered from symptomatic side effects of radiotherapy or symptoms of autoimmune toxicities related to previous treatment with check-point inhibitors at the time of initiation of screening procedure.

Final 5.0 (incorporating Protocol Amendment 4) 06 Jul 2017

Other cancer/metastases

- 22. Known past or current malignancy other than inclusion diagnosis, except for:
 - o Cervical carcinoma of Stage 1B or less
 - Non-invasive basal cell or squamous cell skin carcinoma
 - o Non-invasive, superficial bladder cancer
 - o Prostate cancer with a current PSA level < 0.1 ng/mL
 - o Breast cancer in BRCA1 or BRCA2 positive ovarian cancer patients
 - \circ Any curable cancer with a CR of > 5 years duration
- 23. Radiographic evidence of cavitating pulmonary lesions.
- 24. Tumor invading any large blood vessel, unless approved by the sponsor Medical Officer.

Other

- 25. Ongoing significant, uncontrolled medical condition
- 26. Presence of CTCAE grade \geq 2 peripheral neuropathy.
- 27. Clinically significant active viral, bacterial or fungal infection requiring:
 - Intravenous treatment with antimicrobial therapy starting less than four weeks prior to first dose, or
 - Oral treatment with antimicrobial therapy starting less than 10 days prior to first dose.
- 28. Known human immunodeficiency virus seropositivity.
- 29. Positive serology (unless due to vaccination or passive immunization due to Ig therapy) for hepatitis B defined by:
 - o Positive test for HBsAg (hepatitis B surface antigen) and/or
 - Positive test for anti-HBs and anti-HBc (antibodies to hepatitis B surface and core antigens).
- 30. Positive serology for hepatitis C based on test at screening.
- 31. Inflammatory bowel disease including Crohn's disease and colitis ulcerosa.
- 32. Inflammatory lung disease including moderate and severe asthma and chronic obstructive pulmonary disease (COPD) requiring chronic medical therapy.
- 33. Ongoing acute or chronic inflammatory skin disease.
- 34. Ophthalmological:
 - o Active ocular surface disease at baseline (based on ophthalmological evaluation).
 - o History of cicatricial conjunctivitis (as evaluated by an ophthalmologist).

Final 5.0 (incorporating Protocol Amendment 4) 06 Jul 2017

8.3.3 Patient Allocation Procedure

Allocation of patients will be controlled by the CRO.

When a potential patient is identified at a site, the site personnel must contact the CRO for allocation in accordance to Section 8.4.9.5. If there is an opening in the currently enrolling cohort, the site will be given approval to start the screening process.

If there is no opening in the currently enrolling cohort, the CRO will place the patient on a list of potential patients. If another patient fails the screening process, the CRO will alert the site that has the next patient on the waiting list. If the patient is still eligible, the site will be given approval to start the screening process.

8.3.4 Withdrawal and Replacement of Patients

8.3.4.1 Criteria for Patient Withdrawal from Treatment

Patients will be withdrawn from treatment for the following reasons:

- DLT/DLT-equivalent events (see Section 8.4.8 for specification, exception and dose modifications).
- > 2 dose reductions due to recurrent toxicities possibly related to tisotumab vedotin (HuMax-TF-ADC) (see Sections 8.4.5.1, 8.4.5.2, and 8.4.5.3).
- CTCAE grade \geq 3 macular-papular skin rash.
- CTCAE grade 1 treatment-related bullous dermatitis or skin bullae (blister) ≥ 0.5 cm.
- Recurrent CTCAE grade 4 neutropenia may be withdrawn, see Section 8.4.5.2.
- CTCAE grade 3 QTcF interval prolongation (≥ 501 msec on at least two separate ECGs).
- First recurrence of CTCAE grade ≥ 3 conjunctivitis (despite dose reduction, see Section 8.4.5.3)
- Third recurrence of CTCAE grade ≤ 2 keratitis (despite dose reductions, see Section 8.4.5.3)
- First occurrence of CTCAE grade \geq 3 keratitis
- Ophthalmological evaluation reveals conjunctival/corneal scarring
- Any grade of symblepharon
- Any grade of fluorescent patches or conjunctival ulceration that does not stabilize or improve after dose reduction
- Any dose delay related to ocular toxicity exceeding 12 weeks

Final 5.0 (incorporating Protocol Amendment 4) 06 Jul 2017

- Dose delay of more than two weeks due to toxicity possibly related to tisotumab vedotin (HuMax-TF-ADC) (except for dose delays due to neuropathy, skin rash, keratitis and conjunctivitis)*.
- Pregnancy.
- Patient choice.
- Investigator or sponsor decision.
- * The exception is due to the fact that decrease to CTCAE grade 1 intensity for neuropathy, skin rash, keratitis and conjunctivitis may last for more than two weeks.

8.3.4.2 Criteria for Patient Withdrawal from the Trial

Patients will be withdrawn from the trial at any time for any of the following reasons:

- Patient choice.
- Investigator or sponsor decision.
- Initiation of new anti-cancer treatment.
- Lost to follow-up.
- Intercurrent illness that precludes further participation or requires a prohibited concomitant treatment.
- Disease progression.

8.3.4.3 Evaluations at Withdrawal from Treatment

When a patient withdraws from treatment, he/she should return for follow-up visits and the End of Treatment page must be filled in.

8.3.4.4 Evaluations at Withdrawal from the Trial

When a patient withdraws from the trial, investigators should attempt to obtain information and perform an EOT Visit and a 30 day Safety Follow-up Visit. The EOT Visit should be performed as soon as possible and prior to initiation of new treatment and will include most assessments performed at the Screening Visit, and response assessments (Section 12.5.3).

In the Dose Escalation part of the trial, the Safety Follow-up Visit should only be performed if the patient withdraws before attending Follow-up Visit 1. Only SAEs will be assessed at the Safety Follow-up Visit. For patients considered as lost to follow-up, the investigator should make an effort (at least one phone call or one written message to the patient), and document his/her effort (date and summary of the phone call or copy of the written message in the source documents), to complete the final evaluation. All results of these evaluations and observations, together with a narrative description of the reason(s) for removing the patient, must be recorded in the source documents. The primary reason for withdrawal will be recorded in the eCRF on End of Trial page.

Final 5.0 (incorporating Protocol Amendment 4) 06 Jul 2017

8.3.4.5 Replacement of Patients

Patients who discontinue the trial during the first cycle (28 days) for reasons other than a DLT should be replaced. After implementation of the urgent safety measure (Protocol Amendment 4), no patients will be replaced.

Patients who are withdrawn after the first cycle will not be replaced. However, sufficient number of patients will be enrolled to ensure the minimum sample size defined (see Section 12.9).

8.4 Treatment

The Dose Escalation part of the trial must be run in phase I units with cardiopulmonary resuscitation rescue equipment available and fast access to emergency units. Throughout the infusion patients will be under surveillance by trial personnel. The physician supervising the trial drug infusion must be readily accessible for assistance during the day of infusion.

Tisotumab vedotin (HuMax-TF-ADC) is an antibody drug conjugate composed of an IgG1 human monoclonal antibody (HuMax-TF) chemically conjugated via a protease cleavable vc linker to the drug MMAE.

Tisotumab vedotin (HuMax-TF-ADC) is presented as a lyophilized cake for reconstitution in water for injection and is intended for dosing by the intravenous route by infusion after dilution in physiological saline solution.

8.4.1 Treatments Administered

The investigator must ensure that the trial drug will be used only in accordance with the protocol.

Tisotumab vedotin (HuMax-TF-ADC) will be administered as an intravenous infusion on Days 1, 8 and 15 of each cycle (one treatment cycle is 28 days).

After implementation of the urgent safety measure (Protocol Amendment 4), tisotumab vedotin (HuMax-TF-ADC) 2.0 mg/kg will be administrated once q3wk on Day 1 (one treatment cycle is 21 days), regardless of the prior dose(s) administered. The next dose of tisotumab vedotin (HuMax-TF-ADC) cannot be administered until at least 21 days have elapsed since the last administration.

Each patient's dose will be calculated based on the patient's weight rounded to the nearest kilogram, i.e., assigned cohort dose in mg/kg × body weight in kg. The weight used per cycle should be the weight taken in connection with the first dosing visit of the current cycle (see Section 10.3). For patients whose body mass index (BMI) is greater than 30 kg/m², the investigator should use a weight that, based on the patient's height, corresponds to a maximum BMI of 30.

The dose is calculated according to the following formula if BMI is greater than 30kg/m²:

Dose
$$(mg) = x (mg/kg) * 30 (kg/m2) * height (m) * height (m)$$

Final 5.0 (incorporating Protocol Amendment 4) 06 Jul 2017

Tisotumab vedotin (HuMax-TF-ADC) will be administered over a minimum of 30 minutes. If infusion-related events emerge, refer to Section 8.4.4. The infusion is complete when the infusion line has been flushed with a minimum 15 mL saline. Preventive eye therapy should be administered in relation to infusions as detailed in Section 8.4.5.3.

8.4.2 Trial Treatment Preparation

The dose of tisotumab vedotin (HuMax-TF-ADC) for administration must be prepared by the site pharmacy using aseptic technique. Tisotumab vedotin (HuMax-TF-ADC) will be supplied to the site/pharmacy as bulk supply cartons.

The IMP will be supplied in vials containing 40 mg of tisotumab vedotin (HuMax-TF-ADC) as lyophilized powder. The powder should be reconstituted with 4 mL water for injection leading to a 10 mg/mL solution.

The reconstituted tisotumab vedotin (HuMax-TF-ADC) should be diluted into 0.9% NaCl 100 mL infusion bag according to the dose assigned to the patient.

Tisotumab vedotin (HuMax-TF-ADC) (lyophilized vials) should be stored in a refrigerator at 2°C to 8°C.

The infusion must be completed within 24 hours after the tisotumab vedotin (HuMax-TF-ADC) vials have been reconstituted. An in-line filter must be used for the infusion. The entire 100 mL infusion volume from the prepared infusion bag needs to be administered, no dead volume is provided.

Please refer to the Pharmacy Manuals for instructions on storage, preparation and infusion. Labeling will be in accordance with the European Union (EU) Guidelines to Good Manufacturing Practice, Annex 13, Investigational Medicinal Products, and any other applicable local regulatory requirements.

8.4.3 Trial Treatment Storage and Accountability

It is forbidden to use investigational drug material for purposes other than as defined in this protocol.

8.4.3.1 Trial Treatment Storage

Tisotumab vedotin (HuMax-TF-ADC) will be stored at 2°C to 8°C in a secure area with restricted access.

8.4.3.2 Trial Treatment Accountability

The trial drug must exclusively be used for the investigation specified in this protocol and will only be accessible to authorized staff. The investigator or designee must confirm and document the receipt of the trial drug.

Vials must be kept at the pharmacy. Throughout the trial, all used and unused material will be accounted for. Documented destruction of drugs and containers should be coordinated at the clinical site. One copy of the destruction certificate must be kept in the investigator's file and the other copy must be sent to the sponsor representative.

Final 5.0 (incorporating Protocol Amendment 4) 06 Jul 2017

8.4.4 Treatment of Infusion-Related Reactions

In the initial patients, few infusion-related reactions, all being CTCAE grade 1, have been reported during the Dose Escalation part of the GEN701 trial. However infusion-related reactions have been observed in one animal during the pre-clinical studies and with other cleavable MMAE based ADCs. Patients should therefore be monitored during infusion.

- If an infusion-related reaction occurs, the infusion should be interrupted and appropriate medical management instituted. The infusions may be restarted at the investigator's discretion.
- Patients who have experienced prior infusion-related CTCAE grade ≥ 3 reactions in the trial should be pre-medicated before all subsequent infusions with an antihistamine and/or acetaminophen and/or corticosteroid at the investigator's discretion.
- If anaphylaxis occurs, administration of trial drug should be discontinued immediately and permanently and appropriate medical therapy should be administered.

8.4.5 Dose Modification and Mitigation Plans

Dose modifications should be preapproved by the sponsor Medical Officer. Below the dose modification and mitigation plans are specified according to the once q3wk treatment scheme:

8.4.5.1 Dose Modification and Mitigation Plan for Skin Toxicity

- Ongoing, acute or chronic inflammatory skin disease is an exclusion criterion in this trial (see Section 8.3.2).
- Frequent assessments of skin should be performed during Cycle 1:
 - o At Days 1 and 15.
- Assessment of skin during the remaining cycles will be performed on Day 1 in each cycle before dosing.
- Patients' information to include information about potential skin toxicity and patients will be instructed to contact the investigator and/or the site dermatologist in case of skin rash, pruritus or bullae.
- Investigators will be trained in skin monitoring and action to findings.
- Dose adjustment for skin toxicity should be managed as follows:
 - o For CTCAE grade 1 macular-papular skin rash: Continue dosing of tisotumab vedotin (HuMax-TF-ADC) as planned, treat with a potent topical steroid (betamethasone valerate or equivalent) once daily for up to one week, facial areas with a moderate topical steroid (hydrocortisone butyrate 0.1% or equivalent) twice daily for up to one week; thereafter every other day for a maximum of three weeks.
 - For CTCAE grade 2 macular-papular skin rash: Postpone dosing of tisotumab vedotin (HuMax-TF-ADC) until skin rash has decreased to grade 1, then continue dosing of tisotumab vedotin (HuMax-TF-ADC) as planned. Treat the skin rash with

Final 5.0 (incorporating Protocol Amendment 4)

a potent topical steroid (betamethasone valerate or equivalent) once daily for up to one week; facial areas with a moderate topical steroid (hydrocortisone butyrate 0.1% or equivalent) twice daily, followed by dosing once every other day for a maximum of three weeks.

- o For CTCAE grade ≥ 3 macular-papular skin rash: Stop dosing (patient withdrawal) and treat the skin rash with a potent topical steroid (betamethasone valerate or equivalent) once daily for up to one week, followed by dosing once every other day for a maximum of three weeks.
- Vesicular skin reaction: postpone dosing until recovery and continue on half dose until the end of treatment period.
- Withdrawal criteria for skin toxicity:
 - o Patients with CTCAE grade \geq 3 macular-papular skin rash (covering \geq 30% of body surface area [BSA]).
 - o Patients with TEN, Steven Johnson and CTCAE grade ≥ 3 cutaneous vasculitis.
 - Patients with CTCAE grade 1 treatment-related bullous dermatitis or skin bullae (blister) > 0.5 cm.

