10.12 Skin Assessments

Development of skin reactions will be monitored during the trial and registered on a separate form. A Dermatologist must be available for consulting at each site.

Rash should be reported and graded according to the NCI-CTCAE for macular-papular skin rash according to Table 8 below:

Table 8: Grading of Skin Rash

System Organ Class	Event	Grade 1	Grade 2	Grade 3	Grade 4	Grade 5
Skin and subcutaneou s tissue disorders	Rash maculo- papular	Macules/pap ules covering < 10% BSA with or without symptoms (e.g., pruritus, burning, tightness)	Macules/pap ules covering 10-30% BSA with or without symptoms (e.g., pruritus, burning, tightness); limiting instrumental activities of daily living	Macules/pap ules covering > 30% BSA with or without associated symptoms; limiting self-care activities of daily living	Life- threatening	Death

BSA=Body Surface Area

In case of bulla/bullae, these should be measured and reported as AEs.

Final 5.0 (incorporating Protocol Amendment 4) 06 Jul 2017

Patients should be withdrawn if they experience a trial drug-related grade ≥ 3 macular-papular skin rash (covering $\geq 30\%$ of BSA), bullae (skin blisters ≥ 0.5 cm) or TEN, Steven Johnson or grade ≥ 3 cutaneous vasculitis.

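### The skin-toxicity withdrawal rules in Protocol Sections 8.3.4.1, 8.4.5.1 and 10.12 do not agree, and the bullous rule names grade 1 only

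*Protocol*

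**What the plan says.** Three sections of the Protocol tell a site when a skin event ends treatment.

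- **Section 8.3.4.1** (withdrawal from treatment) lists grade ≥ 3 macular-papular rash, with no body-surface figure and no relatedness condition. It also lists "CTCAE grade 1 treatment-related bullous dermatitis or skin bullae (blister) ≥ 0.5 cm". TEN, Stevens-Johnson syndrome and cutaneous vasculitis are not named. They enter through the first item of the list, DLT or DLT-equivalent events, which points to Section 8.4.8.
- **Section 8.4.5.1** (skin mitigation plan) lists grade ≥ 3 rash, explained as at least 30% of body surface and with no relatedness condition. It names TEN, Stevens-Johnson and grade ≥ 3 cutaneous vasculitis outright. Its bullous item is "Patients with CTCAE grade 1 treatment-related bullous dermatitis or skin bullae (blister) > 0.5 cm".
- **Section 10.12** (skin assessments) begins its rule with "Patients should be withdrawn if they experience a trial drug-related grade ≥ 3 macular-papular skin rash", again explained as at least 30% of body surface, and continues with "bullae (skin blisters ≥ 0.5 cm) or TEN, Steven Johnson or grade ≥ 3 cutaneous vasculitis". It gives no grade for bullous events and does not mention bullous dermatitis. Table 8 in the same section places 10-30% of body surface in grade 2; its grade 3 entry reads "covering > 30% BSA with or without associated symptoms".

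Two other places bear on this. Section 8.2.1 says that the criteria for individual patients are those of Section 8.3.4. Section 8.4.8 lets the DMC and the Safety Committee keep a patient with a DLT on the trial, possibly at a reduced dose.

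**The concern.** These are stopping rules, and a site may reasonably open any of the three sections when a skin event occurs. If they differ, the decision to continue depends on which page was read. The bullous item raises a further question: it carries a bare grade 1, although the rash and vasculitis items beside it in 8.4.5.1 are written as a grade or higher. Taken literally it stops the mildest grade and leaves the higher ones to other provisions.

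Skin disorders are a named secondary endpoint (Section 7.2.2) and are summarized separately (Section 12.5.1). Uneven stopping would bear first on patient safety, then on discontinuations attributed to skin toxicity and on the exposure time against which events are read.

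**Working it through.** No sample size, power or error rate is involved. The check applies each rule literally to the same event and compares the outcomes.

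**Bullous events.** Assume the event is drug-related, and read the blister-size limb as independent of grade. The table shows whether the bullous item itself leads to withdrawal.

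| Event | 8.3.4.1 | 8.4.5.1 | 10.12 |
|---|---|---|---|
| Grade 1 bullous dermatitis, 0.4 cm blisters | yes | yes | not covered |
| Grade 2 or 3, 0.4 cm blisters | not covered | not covered | not covered |
| Grade 2 or 3, 0.5 cm bulla | yes | not covered | yes |
| Any grade, 0.6 cm bulla | yes | yes | yes |

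The first two rows carry the point. With identical blisters, the grade 1 event is stopped in two sections and the higher-grade event meets no bullous item in any of them. If grade 1 is instead read as governing the size limb too, the larger-blister higher-grade events also fall outside 8.3.4.1 and 8.4.5.1. The third row turns only on ≥ 0.5 cm versus > 0.5 cm. Section 8.4.5.1 also keeps patients with a vesicular skin reaction on treatment at a reduced dose after recovery, without saying where a vesicle ends and a bulla begins.

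**Rash.**

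| Body surface | Table 8 grade | 8.3.4.1 | 8.4.5.1 | 10.12 |
|---|---|---|---|---|
| 29% | 2 | no | no | no |
| 30% | 2 | no | meets the area figure, not the grade | meets the area figure, not the grade |
| 31%, drug-related | 3 | yes | yes | yes |
| 31%, not drug-related | 3 | yes | yes | not covered |

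The last row is a difference of substance. The 30% row is a boundary case: for a grade 2 rash, 8.4.5.1 says to postpone dosing and then continue, yet the same area satisfies the figure attached to its withdrawal criterion.

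**TEN, Stevens-Johnson, grade ≥ 3 cutaneous vasculitis.** Section 8.4.5.1 withdraws with no exception stated, and 10.12 lists them for withdrawal. In 8.3.4.1 they are reached through the dermatologic row of Table 7 in 8.4.8. That table covers events at least possibly related to the drug, and the section permits a patient with a DLT to continue. The routes therefore differ on whether continuation is possible at all.

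**The case against.** The strongest reply is that a governing list exists. Section 8.2.1 names Section 8.3.4 as the place for individual withdrawal criteria, and 10.12 is a methods section that does not claim to be complete. On that view, where 10.12 omits something, 8.3.4.1 decides. This has force: 10.12 never says to keep a patient with an unrelated grade ≥ 3 rash on treatment. A reader might infer that the sections give opposite instructions; the text supports only that one is silent where the others speak.

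A reader might also infer that higher-grade bullous events have no stopping rule at all. That goes too far. The size limb, read on its own, catches those with larger bullae. Table 7 includes related grade ≥ 3 non-hematological events that the DMC regards as medically important, and 8.3.4.1 allows withdrawal by investigator or sponsor decision. A clinician may well take grade 1 as the entry threshold.

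The differences in size and area are thin. The > against ≥ sign may come from the reading of the PDF and matters only at exactly 0.5 cm. The area figure is a parenthesis to a grade, and matters only at exactly 30%.

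What these replies do not cure is the grade 1 wording, because it sits in the governing list itself. The backstops work case by case, and the Table 7 item does not reach a grade 2 event. Nor does naming 8.3.4.1 as the control list settle TEN, Stevens-Johnson and vasculitis: it would replace the unconditional rule of 8.4.5.1 with one that allows an exception.

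**Conclusion.** The point holds as an inconsistency between stopping rules that should be corrected. Three differences are substantive: the bare grade 1 in the bullous item of 8.3.4.1 and 8.4.5.1, with no counterpart in 10.12; the relatedness condition for grade ≥ 3 rash in 10.12 alone; and the different routes for TEN, Stevens-Johnson and grade ≥ 3 cutaneous vasculitis. The 0.5 cm and 30% mismatches are minor, and the conclusion does not rest on them.

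The size cannot be put as a number of patients, because the protocol gives no expected frequency of these events. Under the assumptions stated above, the literal gap in the bullous rule is a related event above grade 1 with blisters below 0.5 cm. No inference is at risk: there are no formal tests, all exposed patients are analyzed, and skin events are counted whether or not the patient is withdrawn. The consequence is uneven stopping between sites, with a knock-on effect on discontinuations and exposure time.

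**What to change.** Reconcile the three passages into one skin withdrawal list in Section 8.3.4.1, and have 8.4.5.1 and 10.12 refer to it without restating it. The list should state once:

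- which grades of bullous dermatitis it covers, and whether the blister-size limb applies independently of grade;
- the blister limit, including which side the boundary value falls on;
- whether drug-relatedness is required, item by item;
- a body-surface boundary that matches Table 8;
- whether the continuation exception for DLTs in 8.4.8 applies to TEN, Stevens-Johnson syndrome and grade ≥ 3 cutaneous vasculitis.

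Which value applies in each case is for the sponsor's clinical team to decide. The cost is wording in the next amendment, with no change to data collection or analysis.
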